--	--

	
collect information, but no decision will be made from the results of the finger stick.
 
If the HMS recommends giving CHO to the subject, the investigator will follow the recommendation. Any other outside intervention by the investigator will terminate the study session for that subject. If clinical results from a subject are found to be suboptimal with excessive hyperglycemia or excessive hypoglycemia alarms, the responsiveness factor of the control algorithm may be adjusted for the study of the next subject.
 
Once the glucose level of the patient is back to more than 90 mg/dL for more than 1 hour, and the glucose level is less than 180 mg/dL with ketones less than 0.6 mmol/L, the patient will be discharged from the CRC.
 
On the day following the CRC visit, the study staff will be in contact, by telephone or in person with the subject for follow-up.

Subject Population	
Adults aged 21-65 years                      Type 1 diabetes mellitus for at least one year                      Using an insulin infusion pump with rapid acting insulin for at least six months

Sample Size	12 to 20 subjects
Duration of the subject participation	Total duration by each subject is expected to be approximately one week from time of contact to review glucose control to follow-up after discharge from CRC visit.
Study Center	Sansum Diabetes Research Institute, Santa Barbara, CA

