**Table 10–2: Safety action to take in case of hypoglycemic and hyperglycemic events based on YSI values**

CONDITION	ACTION
Hyperglycemia	
Asymptomatic and serum glucose > 250 mg/dL more than 2 hours Or if subject develops nausea, vomiting or abdominal pain	Test the blood for serum ketones. Check the pump, if not running, change pump. If blood ketones exceed 1.0 mmol/L, the study for this subject will be terminated. If a correction bolus needs to be administered by the study staff, it will be administered with a syringe.
Mild polyuria and polydipsia; serum glucose > 250 mg/dL more than 3 hours	If blood ketones were less than 0.6 mmol/L at 2 hours, recheck blood ketones and check the pump. If pump not running or catheter occluded or leaking, change the pump. If blood ketones > 1.0 mmol/L, then the study for this subject will be terminated. If a correction bolus needs to be administered by the study staff, it will be administered with a syringe.
Glucose level $\geq$ 300 mg/dL for more than 1 hour	Investigator will give a manual correction dose bolus administered with a syringe. The trial will be terminated for this subject.
Emesis, but with a normal sensorium and glucose > 350 mg/dL	The study for this subject will be terminated. Intravenous fluids would be given at a rate of 3,000 cc/M2/day. A manual correction dose of a short acting insulin analog would be given. The insulin infusion set would be changed. The subject would remain in the CRC until serum glucose is < 200 mg/dL. Subject will be monitored for at least 2 hours post treatment by study investigator. In case of reoccurring symptoms the subject shall be transferred to the emergency room by paramedics. If a correction bolus needs to be administered by the study staff, it will be administered with a syringe.
Decreased sensorium (sleepy, difficult to arouse) with or without emesis: glucose > 350 mg/dL	The study will be terminated for this subject. The subject will be transferred to the emergency room for evaluation with electrolytes and pH and monitoring for possible further deterioration of neurological status as a decrease sensorium may be indicative of electrolyte and/or pH abnormalities that could lead to respiratory or cardiac depression if not detected and treated appropriately.
Blood glucose >400 mg/dL	The study is terminated for this subject. The investigator will give a manual (with a syringe) correction bolus.

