#### 11.4. **Stopping rules**

##### 11.4.1. **Criteria for individual subject withdrawal**

The termination of a subject from the study will be documented in the subject source documents and on the CRF. The reason for the termination and possible following effects must be documented. Subjects that have discontinued participation will not be replaced. Should a subject be lost-to-follow-up (LTF), i.e. no return for the on-site 24-hour closed-loop after enrollment, a reasonable effort will be made to contact the subject to determine why the subject failed to return. Any investigator-decided outside intervention will trigger termination of the trial for the subject. If the investigator treats the subject with 16 g of carbohydrates following the recommendation of the HMS, then the trial will not be terminated, this is anticipated and part of the trial. If a trial is terminated, the same subject may be rescheduled and the trial repeated. Rules for terminating a visit for an individual subject are as follows (glucose levels measured by YSI).

- Outside intervention (bolus or carbohydrate treatment) from the investigator that did not follow recommendation from HMS.
- Gross system malfunctions such as:
  - Pump failure
  - Failure of both study sensors
  - System or controller malfunctions that may have an impact on the safety of the subject
- Any correction bolus initiated by the investigator.
- Glucose YSI > 250 mg/dL for more than 2 hours and blood ketones exceed 1.0 mmol/L.
- Subject develops nausea, vomiting, or abdominal pain and blood ketones exceed 1.0 mmol/L.
- Glucose YSI > 350 mg/dL with decreased sensorium with or without emesis.
- Glucose level YSI > 400 mg/dL at any point if the investigator decides to treat with a correction bolus.

- Glucose YSI < 60 mg/dL without having received a HMS warning
- Glucose YSI < 50 mg/dL.
- Severe Hypoglycemia or Hyperglycemia as defined by Table 9-2.
- The subject or physician requests the trial be stopped.
- Failure of YSI equipment.
- Subject withdraws his/her consent.
- Adverse Event which necessitates termination of the study as decided by the investigator, such as DKA.
- Protocol violation: subject is no compliant with procedures, becomes pregnant, violates study entry criteria, or use unacceptable medication.

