**Table 15–2: Levels of hyperglycemia and hypoglycemia as defined by YSI**

Severity	YSI	Clinical symptoms	Description
Hyperglycemia			
Negligible	200<BG<300 mg/dl for <1 hr or BG>300 mg/dl for <1 hr	Asymptomatic	Little or no potential injury, pain or discomfort
Mild	200<BG<300 mg/dl	Mild polydipsia and mild polyuria	Potential of minor injury, pain, or user discomfort
Moderate	BG> 300 mg/dl	Symptoms of ketosis (nausea, polyuria, polydipsia, vomiting) with normal mental status	Potential of non-life threatening injury, pain, or direct or indirect exacerbation of existing non-life threatening condition
Severe	BG>300 mg/dL requiring intravenous fluids to correct	Altered mental state Subject in critical condition	Major injury requiring medical intervention
Very severe	N/A	No heart rate, no blood pressure Subject in critical condition	Potential of death or serious injury
Hypoglycemia			
Negligible	60<BG<70 mg/dL	Asymptomatic or adrenergic/cholinergic symptoms without neurocognitive changes	Little or no potential injury, pain or discomfort
Mild	BG<60 mg/dL Or HMS indicates impending hypoglycemia (<70mg/dL in the next 15 min per CGM measurements)	Asymptomatic or adrenergic / cholinergic symptoms without neurocognitive changes	Potential of minor injury, pain, or user discomfort
Moderate	BG<60 mg/dL	Subject is talking, but early neurocognitive changes such as slow speech, mild affect changes	Non-life threatening injury, pain, or direct or indirect exacerbation of existing non-life threatening condition
Severe	BG<60 mg/dL	Require assistance of another individual due to loss of consciousness, seizure or the inability to administer treatment to self due to neuroglycopenia	Major injury requiring medical intervention
Very Severe	N/A	No heart rate, no blood pressure Subject in critical condition	Potential of death or serious injury

[Table 15–3](#)~~Table 9–3~~ is a list of anticipated adverse events. These will be reported on the CRF found in Appendix 9 of the IDE submission.

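### Table 10–2 orders the 3-hour ketone recheck and pump check only if 2-hour ketones were below 0.6 mmol/L, so a symptomatic subject at 0.6–1.0 mmol/L, or with no 2-hour value, gets neither order

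*Combined protocol and SAP*

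**What the plan says.** Two rows of Table 10–2 (section 10.4.2.3) matter here.

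- **Row 1.** The glucose trigger is "Asymptomatic and serum glucose > 250 mg/dL more than 2 hours"; new nausea, vomiting or abdominal pain is a second trigger. The action is "Test the blood for serum ketones", together with a pump check. Neither step depends on an earlier ketone value. The session ends if ketones exceed 1.0 mmol/L.
- **Row 2.** The trigger is "Mild polyuria and polydipsia; serum glucose > 250 mg/dL more than 3 hours". The action begins "If blood ketones were less than 0.6 mmol/L at 2 hours, recheck blood ketones and check the pump". Two further sentences carry no ketone condition: one says when to change the pump, and the other is the stop, "If blood ketones > 1.0 mmol/L, then the study for this subject will be terminated".

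Section 11.4.1 repeats the stop as a withdrawal criterion: "Glucose YSI > 250 mg/dL for more than 2 hours and blood ketones exceed 1.0 mmol/L". The 0.6 mmol/L cut-off appears elsewhere only as a discharge limit. The synopsis puts it as "the glucose level is less than 180 mg/dL with ketones less than 0.6 mmol/L, the patient will be discharged from the CRC", and sections 10.1 and 10.4.5 agree.

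**The concern.** Row 2 should catch ketones that rise while glucose stays high. As written, it retests the subject whose 2-hour ketones were lowest and orders no retest for the one whose ketones were closer to the stopping limit. That second subject also has a longer episode than at the first test and now has symptoms. The row's stop above 1.0 mmol/L needs a current ketone value, and its pump-change sentence needs a pump check, yet neither is ordered for this subject.

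The protocol itself treats 0.6 mmol/L as meaningful: a subject at 0.6–1.0 does not meet the discharge limit. What is at stake is the safety procedure for one uncommon state. No estimate, endpoint or sample size depends on it.

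**Working it through.** The plan gives no figure to reproduce. The check divides subjects by their 2-hour ketone value and reads off what is ordered at each time.

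**Inputs.** Let k be blood ketones (mmol/L) at 2 hours. The recheck condition is k < 0.6 (row 2). The stop is k > 1.0 (rows 1 and 2, section 11.4.1). Row 1's triggers are as described above.

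| State at 2 hours | Row 1 at 2 hours | Row 2 after 3 hours, with mild polyuria and polydipsia |
|---|---|---|
| k < 0.6 | tested, pump checked, continues | recheck and pump check ordered |
| 0.6 ≤ k ≤ 1.0 | tested, pump checked, continues | neither ordered |
| k > 1.0 | tested, terminated | not reached |
| no value: polyuria and polydipsia already present, without nausea, vomiting or abdominal pain | neither trigger met, read literally | condition cannot be met; neither ordered |

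**Distance to the stop.** The uncovered band is 1.0 − 0.6 = 0.4 mmol/L wide. A subject in it is at most 0.4 below the limit, whereas every subject with an ordered recheck is more than 0.4 below it.

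**Timing.** The missing test falls about 3 − 2 = 1 hour after the first. For the subject with no 2-hour value it would be the first ketone test of the episode.

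**Does another rule supply the test?**
- Table 10–1 schedules glucose measurements only.
- Section 11.4.1 uses a ketone value but orders none.
- The discharge rules (synopsis, sections 10.1 and 10.4.5) call for ketones only after closed-loop has ended.
- Row 1's symptom trigger does not include polyuria or polydipsia.

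None orders a 3-hour test for these subjects.

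**Glucose range.** Row 2 needs more than 250 mg/dL, and another row of Table 10–2 ends the session at 300 mg/dL or above for more than 1 hour. The affected subject is therefore essentially at 250–300 mg/dL.

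**Frequency.** The documents give no rate for glucose above 250 mg/dL lasting 3 hours. The nearest figures are the predecessor study's mean times above 180 mg/dL in the 5 hours after a meal (Table 3–1):
- dinner: 0.28 × 5 h = 1.4 h
- breakfast: 0.35 × 5 h = 1.75 h

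These are means at a lower threshold and say little about the tail. That study also had no inhaled insulin and a smaller breakfast. They are consistent with the state being uncommon but do not give a rate.

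**The case against.** The best defence is that row 2 was not meant this way. It takes a 2-hour ketone value for granted, which makes most sense if row 1 was meant for anyone above 250 mg/dL for more than 2 hours, with or without symptoms. The withdrawal rule in section 11.4.1 has no symptom qualifier, which supports that view. If row 1 keeps applying, its unconditional test still reaches the subject at 0.6–1.0. The opening clause may also have been meant as *even if* ketones were below 0.6. Row 2's later sentences are not limited by ketone level, which suggests that a check for everyone was assumed.

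This is a reasonable account of intent, but it is inference. The text says *if*, and row 1's glucose trigger is limited to asymptomatic subjects. The table exists to tell staff what to do, and on its face it withholds the order.

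The defence is stronger on consequence, and that part stands:
- A physician is present throughout and can test at discretion.
- Plasma glucose is read at least every 30 minutes.
- Row 1 orders a pump check at 2 hours whatever the ketone level, for subjects who meet its trigger.
- Nausea, vomiting or abdominal pain prompts a ketone test.
- Sustained glucose of 300 mg/dL or more, or any value above 400, ends the session under Table 10–2.

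Table 15–2 does list polyuria and polydipsia under "Symptoms of ketosis (nausea, polyuria, polydipsia, vomiting) with normal mental status", but in its row for glucose above 300 mg/dL. At 200–300 mg/dL it grades mild polyuria and polydipsia as mild hyperglycaemia. These points limit the harm; none of them orders the missing recheck.

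**Conclusion.** The point holds as a minor gap in a written safety rule. Read literally, row 2 orders no 3-hour ketone recheck or pump check for a symptomatic subject with 2-hour ketones of 0.6–1.0 mmol/L, nor for one already symptomatic at 2 hours who has no 2-hour value. The size is one ketone test and one pump check at about 3 hours, in few and possibly none of 12–20 subjects. The no-value case rests on the literal reading of *asymptomatic* in row 1. The frequency is a judgement, because the documents give no rate.

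Three stronger conclusions might be inferred, and the documents do not support them:

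- *Row 2 gives these subjects no instruction at all.* Its pump-change sentence and its stop above 1.0 mmol/L still apply. What is missing is the order for the checks that they presuppose.
- *The clause leaves these subjects without a ketone test until discharge, many hours later.* A subject below 0.6 who is rechecked at 3 hours has no further scheduled test before discharge either. The clause accounts only for the single 3-hour check.
- *Asymptomatic subjects are affected too.* Row 1's test has no ketone threshold, so it does not treat the ketone bands differently.

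**What to change.** In row 2 of Table 10–2, delete the opening condition (everything before the comma in the sentence quoted under the plan's wording), so that the action starts: recheck blood ketones and check the pump. It then applies to every row 2 subject not already terminated, including one with no 2-hour value. Keep the stop above 1.0 mmol/L, which matches section 11.4.1. The edit is right whichever meaning the authors intended.

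The cost is one deleted clause in an amendment, communicated to FDA and the IRB as section 3.1 already provides, and an extra ketone test and pump check in at most a few subjects. No staff, equipment, endpoint or sample size changes.

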## 10.4.2. Monitoring

### 10.4.2.1. *On-going monitoring*

During the closed-loop phase of the study, the following personnel will be present:

- Study coordinator
- Study engineer
- Study physician

Blood glucose level will be measured using a YSI 2300 Stat at a minimum of every 30 minutes ( $\pm 10$  min) and as described by [Table 10-1](#)~~Table 4-1~~. The study physician may request more frequent measurements for safety. If the subject reports symptoms of hypoglycemia, the blood glucose level will be measured with YSI and hypoglycemia guidelines will be followed. The YSI will be used according to manufacturer's instructions and operated by trained study staff. The YSI will be checked a minimum of every 2 hours with the 180 mg/dL standard and recalibrated if YSI glucose standard reads outside the range of 177-183 mg/dL or as needed. All plasma glucose samples will be read on 2 membranes and discrepancies in values that exceed 5 mg/dL will be called to attention of the study physician to assess the need for immediate recalibration.

Each time a YSI measurement is taken, a finger stick measurement using the CONTOUR® EZ blood glucose monitoring system will be taken for information.

Calibration of the CGM will be performed with a finger stick with the CONTOUR® NEXT EZ glucose meter. On the day of CGM insertion and at the beginning of the CRC visit, QC testing of the standard solution specific to the CONTOUR® NEXT EZ glucose meter will be performed. QC may be repeated any time there is a question about the glucose result from the meter. The labeling of the commercially available standard solution can be found in Appendix 13 of the original IDE submission. The QC testing will be performed with at least two different concentrations of control solution, including a concentration in the hypoglycemic range if the manufacturer provides one. A glucose meter will not be used in a study if it does not read within the target range at each concentration per manufacturer labeling.

**Table 10–1:** Frequency of glucose monitoring during CRC

Measurement	When	Frequency
CGM	Closed-loop	Every 5 min
Finger stick OneTouch® Ultra®	Calibration of CGM	Per manufacturer’s guidelines and before meals & at bedtime
YSI + finger stick CONTOUR® EZ	Closed-loop	Every 30±10 min
YSI + finger stick CONTOUR® EZ	If subject reports symptoms of hypoglycemia	When subject reports symptoms of hypoglycemia

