No heart rate, no blood pressure	Perform resuscitation. If this occurred all studies would be put on holding pending an investigation of the circumstances leading to this very adverse outcome. Call 911 and transfer the treated subject to emergency room.
Hypoglycemia	
If CGM prediction is <70 mg/dL in	The AP device notifies the physician. The physician treats the

CONDITION	ACTION
the following 15 min	subject with 16 g of oral CHO. The study is not terminated for this subject. This is an anticipated part of the study. YSI frequency will increase to every 15±5 min until YSI >80 mg/dL.
Adrenergic/cholinergic symptoms without neurocognitive changes; YSI <70 mg/dL, but > 60 mg/dL	Subjects would be closely monitored with glucose levels every 15±5 minutes until YSI > 80 mg/dL. The investigator will give CHO if directed by HMS.
Asymptomatic or adrenergic/cholinergic symptoms with serum glucose < 60 mg/dL	If the HMS did not raise hypoglycemic warning, the study will be terminated for the subject. Subject will be treated with oral simple carbohydrates, such as glucose tablets or juice, and glucose by YSI rechecked in 15 minutes, and treatment repeated if glucose remains < 70 mg/dL. With second treatment the insulin infusion will be suspended until glucose is > 70 mg/dL. YSI frequency will continue every 15±5 min until YSI > 80 mg/dL. Subject will be monitored for at least 2 hours post treatment by study investigator. In case of reoccurring symptoms the subject shall be transferred to the emergency room by paramedics.
Moderate neurocognitive change, subject is talking but unable to treat their hypoglycemia without assistance; serum glucose < 50 mg/dL	The study will be terminated for this subject. This is unlikely to occur because treatment would have been given with first glucose < 60 mg/dL and glucose is measured every 15 minutes. Subjects will be treated with oral simple carbohydrates, such as glucose tablets or juice, and serum glucose subsequently rechecked in 15 minutes, and treatment repeated if glucose remains < 70 mg/dL. With second treatment the insulin infusion will be suspended until glucose is > 70 mg/dL. Subject will be monitored for at least 2 hours post treatment by study investigator. In case of reoccurring symptoms the subject shall be transferred to the emergency room by paramedics.

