Moderate neurocognitive changes, but subject is incoherent and/or refusing treatment and needs assistance for hypoglycemia treatment; serum glucose < 50 mg/dL	The study will be terminated for this subject. This is unlikely to occur because treatment would have been given with first glucose < 60 mg/dL and glucose is subsequently measured every 15 minutes. Intravenous glucose would be given (0.5 grams/kg intravenous over 3 minutes), and insulin delivery suspended until glucose is > 70 mg/dL. Subject will be monitored for at least 2 hours post treatment by study investigator. In case of reoccurring symptoms the subject shall be transferred to the emergency room by paramedics.
Seizure of loss of consciousness; serum glucose < 50 mg/dL	The study will be terminated for this subject. This is unlikely to occur because treatment would have been given with first glucose < 60 mg/dL and glucose is subsequently measured every 15 minutes. Intravenous glucose would be given (0.5 grams/kg intravenous over 3 minutes), and insulin delivery suspended until glucose is > 70 mg/dL. In the event subject experience loss of consciousness or seizure he / she will be transferred to the emergency room by paramedics.
No heart rate, no blood pressure	Perform resuscitation. If this occurred all studies for all subjects would be put on holding pending an investigation of the circumstances leading to this serious adverse event. Call 911 and transfer the treated subject to emergency room.

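### The hypoglycemia rules in Table 10-2, Section 10.4.2.3, the exercise section and Section 11.4.1 give different session outcomes for the same reading, and Table 10-2 has no YSI-based row for neurocognitive signs at 50 to <60 mg/dL

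*Combined protocol and SAP*

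**What the plan says.** Section 10.4.2.3 presents Table 10-2 as the list of safety actions. Its hypoglycemia rows that bear on this point are:

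- A row triggered by a CGM prediction below 70 mg/dL within 15 minutes: 16 g of oral carbohydrate, YSI every 15±5 minutes until above 80, session not terminated. It has no symptom restriction.
- A row for "Asymptomatic or adrenergic/cholinergic symptoms with serum glucose < 60 mg/dL". On the session outcome it says "If the HMS did not raise hypoglycemic warning, the study will be terminated for the subject". It has no lower glucose limit.
- Three rows for neurocognitive signs or seizure, all of which end the session: "Moderate neurocognitive change, subject is talking but unable to treat their hypoglycemia without assistance; serum glucose < 50 mg/dL"; moderate changes where the "subject is incoherent and/or refusing treatment and needs assistance for hypoglycemia treatment; serum glucose < 50 mg/dL"; and "Seizure of loss of consciousness; serum glucose < 50 mg/dL".

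The text of Section 10.4.2.3 adds that carbohydrate taken because the HMS warned is not a device failure and that the trial goes on.

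Section 11.4.1 lists the rules that end a visit. They include a YSI below 60 with no HMS warning, Severe hypoglycemia (by reference to Table 9-2, the old number of Table 15-2), and, with no condition attached, "Glucose YSI < 50 mg/dL". The subject or physician may also stop the trial.

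Table 15-2 grades hypoglycemia. From below 60 mg/dL it calls the event Moderate for "Subject is talking, but early neurocognitive changes such as slow speech, mild affect changes", and Severe when another person's help is needed because of unconsciousness, seizure or inability to self-treat.

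Section 10.4.4 covers a subject who feels hypoglycemic in the exercise segment. If YSI is below 60, carbohydrate is given, closed-loop stops and the trial ends for that subject. The HMS is not mentioned in that rule.

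**The concern.** Staff at the bedside will act from Table 10-2, while the decision to end a visit is also written in Sections 10.4.2.3, 10.4.4 and 11.4.1. If these differ, the same reading can leave a subject on automated insulin delivery or take the subject off it, depending on which page is read. In the 50 to <60 band with neurocognitive signs, a written rule is partly replaced by discretion. Moderate is also the lowest hypoglycemia grade that Section 15.2.5 requires to be documented.

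The data are affected as well. Section 16.1 counts an intervention prompted by the HMS as a successful outcome, while Section 11.4.1 allows a terminated trial to be rescheduled and repeated. One low value could therefore sit in a continuing, successful session or in a terminated one that is run again.

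**Working it through.** The plan gives no figure to reproduce, so the check sets the rules side by side. The inputs are the hypoglycemia rows of Table 10-2, the glucose and severity stops of Section 11.4.1, the grades of Table 15-2 and the exercise rule of Section 10.4.4. Six symptom states were used: asymptomatic; adrenergic/cholinergic; early neurocognitive change without need for help (Moderate in Table 15-2); talking but needing help; incoherent; seizure or loss of consciousness. The last three need assistance and so map to Severe in Table 15-2. Each state was taken with and without an HMS warning.

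| YSI | State | HMS warned | YSI-based row in Table 10-2 | Session under Table 10-2 | Session under 11.4.1 |
|---|---|---|---|---|---|
| 45 | Asymptomatic | Yes | <60 row | Not ended | Ended (<50) |
| 45 | Adrenergic/cholinergic | Yes | <60 row | Not ended | Ended (<50) |
| 45 | Either of these | No | <60 row | Ended | Ended |
| 55 | Early neurocognitive (Moderate) | Yes | None | Prediction row only: not ended | No listed glucose or severity stop |
| 55 | Early neurocognitive (Moderate) | No | None | No row | Ended (<60, no warning) |
| 55 | Three Severe-type states | Yes | None | Prediction row only: not ended | Ended (Severe) |
| 55 | Three Severe-type states | No | None | No row | Ended |

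A value of exactly 50 behaves like 55, because the lower limits are strict.

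**Below 50, warned, no neurocognitive signs.** Two states conflict, asymptomatic and adrenergic/cholinergic. Without a warning the two sources agree. At 50 to <60 they also agree for these two states.

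**50 to <60 with neurocognitive signs.** There are 4 states × 2 warning conditions = 8 combinations, and none has a YSI-based row. Section 11.4.1 ends the 4 unwarned combinations and the 3 warned Severe-type ones, so 4 + 3 = 7 of 8. The remaining 8 − 7 = 1 is the warned Moderate case. For treatment, the 4 warned combinations match the prediction row. The 4 unwarned ones match no row of Table 10-2, and Section 11.4.1 sets no treatment.

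**Exercise.** Take a warned subject at 55 who feels hypoglycemic with adrenergic symptoms. Neither Table 10-2 nor the glucose rules of Section 11.4.1 end the session, but Section 10.4.4 does. Below 50, Sections 10.4.4 and 11.4.1 agree with each other and differ from Table 10-2.

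**Weight of one session.** 1/20 = 5%; 1/12 = 8.3%.

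**The case against.** The best defense is that the texts divide the work: Table 10-2 supplies treatment and Section 11.4.1 supplies termination. On that reading the <60 row is merely silent about a warned subject below 50, the prediction row's instruction not to terminate concerns the warning and not a later YSI value, and the unconditional stop in Section 11.4.1 governs. This is plausible, but the documents do not say it. The <60 row states its own, conditional, session outcome, and the neurocognitive rows state theirs. Section 10.4.2.3 and Section 11.4.1 itself both say that HMS-prompted carbohydrate does not end the trial. No order of precedence is given. For exercise, a different rule may be intended, but the general rules do not mention an exception.

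Three stronger readings are tempting, and the documents do not support them.

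- A reader might infer that neurocognitive hypoglycemia at 50 to <60 has neither treatment nor termination. The prediction row applies to every warned subject whatever the symptoms, Section 11.4.1 ends the Severe and the unwarned cases, and an investigator intervention beyond the HMS recommendation also ends the session. A physician is present throughout, and YSI goes to every 15±5 minutes below 70.
- A reader might infer that Table 10-2 contradicts Table 15-2. Table 15-2 grades severity and assigns no action. The difference between <60 and <50 is a mismatch of thresholds, and the Moderate state in Table 15-2 is milder than the first neurocognitive row of Table 10-2.
- A reader might infer that the neurocognitive rows misstate the sampling interval when they cite 15-minute measurement, because elsewhere "Blood glucose level will be measured using a YSI 2300 Stat at a minimum of every 30 minutes". Two of the three rows make clear that they mean measurement after a first value below 60, and the third has the same lead-in. That fits Table 10-1.

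**Conclusion.** The inconsistency stands, in three parts: two symptom states with opposing session outcomes below 50 after an HMS warning; a 10 mg/dL band with no YSI-based row for neurocognitive signs, within which one combination of eight (Moderate, warned) has no listed glucose or severity stop; and an exercise rule that differs from the general rules after a warning. The direct conflict is with Section 11.4.1. Table 15-2 only shows that the plan itself recognizes these states from below 60.

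This rests on two assumptions. First, Table 10-2 is taken at its word, with no unwritten precedence. Second, states needing assistance are mapped to Severe as Table 15-2 defines it. If the word moderate in the first neurocognitive row were taken as the grade instead, the uncovered combinations would be two of eight.

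The documents give no frequency for these events and do not say how readings after an event enter percent time in range, so the effect on the results cannot be sized beyond the 5% to 8.3% weight of one subject. Close supervision lowers the risk of harm but does not supply the missing rule. The point is more than missing detail, because it decides whether a subject stays on closed-loop insulin.

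**What to change.** Reconcile Section 10.4.2.3 and Table 10-2, the exercise rule in Section 10.4.4, the termination list in Section 11.4.1 and the grades in Table 15-2, so that each combination of YSI value, symptom class and HMS-warning status has one action and one session outcome. In particular:

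- state once whether a YSI below 50 after an HMS warning ends the session;
- assign neurocognitive signs at 50 to <60 to a row, or refer explicitly to the rule that covers them;
- say whether the exercise rule is a deliberate exception;
- say which text governs if two apply.

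The thresholds and the clinical content are for the sponsor and investigator to decide.

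The cost is wording in an amendment, communicated to FDA and the IRB as Section 3.1 provides. Reconciling the text needs no new procedure or measurement. Whether any session ends earlier or later than now implied depends on the rule chosen.
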